Subjects will be randomized to active Naltrexone 25mg, Naltrexone 50mg, and placebo groups in a 1:1:1 ratio using a computer randomization procedure at the CMHC research pharmacy, blind to both research team and subjects. Separate randomization schedules will be applied based on gender, and antipsychotic agent to yield an equal number of male and female subjects in each arm. This is to control for possible differential gender and racial/ethnicity specific effects of Naltrexone on weight as well as differences brought on by higher and lower weight liability medications.

Subjects will take the study medication daily for 52 weeks. Subjects will be seen weekly for the first 4 weeks of the study, thereafter they will be seen on a bi-weekly (every other week) basis to be assessed (i.e. weight, side effect check, paper questionnaires) throughout the remaining 48 weeks of treatment. Compliance will be monitored by pill counts as well as 25mg riboflavin added to the capsules which provides florescence to urine under Wood's lamp (UV or black light). Subjects will be given a study identification card listing the fact that they may be taking naltrexone and this card will include the study emergency cell phone number which will be available 24 hours a day, 7 days per week in case of an emergency.

The study is planned to be run at the Connecticut Mental Health Center (CMHC) and its affiliated satellite clinics throughout the greater New Haven area.

All participants will be carefully assessed with physical examination and laboratory findings, any medical problems that need immediate attention will be referred to each participant's own primary care physician. All potential subjects will meet with study staff for intake and evaluation sessions to determine eligibility prior to enrollment.

A description of assessments is given below:

1) Intake interview including demographics, clinical history, Structured Clinical Interview for DSM-IV (**SCID**) to ascertain diagnosis. 2) Urine toxicology (**Utox**) screen to rule out substance use. The initial sample will also be sent to the lab to confirm opiate results for safety purposes and a follow-up sample will be taken immediately before randomization to study medication to ensure it is negative for opiates; continued random testing will occur at the discretion of the study physician throughout the trial along

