
4. Genetic Testing N/A

A. Describe

- i. the types of future research to be conducted using the materials, specifying if immortalization of cell lines, whole exome or genome sequencing, genome wide association studies, or animal studies are planned
- ii. the plan for the collection of material or the conditions under which material will be received

Assessment Schedule

SCID, Demographics, Physical exam	Week 0
Urine toxicology, pregnancy test for female subjects	Week 0 and every 4 weeks subsequently + as needed
Fluorescence check in urine for compliance	determined by study physician
Fasting Glucose, Insulin, HbA1c, Lipid Profile, Liver function tests	Week 0, 16, 32, 52
Serum leptin, ghrelin, peptide YY, adiponectin, high sensitivity	Week 0, 16, 52
CRP, interleukin 6	
Framingham Score	Calculated same time with blood draws.
Vitals (Blood Pressure, pulse)	Weekly for first 4 weeks, then every two weeks
Weight, BMI	Weekly for first 4 weeks, then every two weeks
RMR, Waist Circumference (WC), 24hr Food Recall, TFEQ, YPAS, BPRS, BDI, QCSRF, QLS, SF-36, C-SSRS.	Week 0 and every 4 weeks
UKU side effects	Weekly for first 4 weeks, then every two weeks
Cognitive Battery	Week 0, Week 16, Week 52

- iii. the types of information about the donor/individual contributors that will be entered into a database
- iv. the methods to uphold confidentiality

- B. What are the conditions or procedures for sharing of materials and/or distributing for future research projects?
- C. Is widespread sharing of materials planned?
- D. When and under what conditions will materials be stripped of all identifiers?
- E. Can donor-subjects withdraw their materials at any time, and/or withdraw the identifiers that connect them to their materials?
 - i. How will requests to withdraw materials be handled (e.g., material no longer identified: that is, anonymized) or material destroyed)?
- F. Describe the provisions for protection of participant privacy
- G. Describe the methods for the security of storage and sharing of materials

5. Subject Population: Provide a detailed description of the types of human subjects who will be recruited into this study.

200 patients with severe mental illness

6. Subject classification: Check off all classifications of subjects that will be specifically recruited for enrollment in the research project. Will subjects who may require additional

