safeguards or other considerations be enrolled in the study? If so, identify the population of subjects requiring special safeguards and provide a justification for their involvement.

 Children	 Healthy	 Fetal material, placenta, or dead fetus
 Non-English Speaking	 Prisoners	 Economically disadvantaged persons
 Decisionally Impaired	 Employees	 Pregnant women and/or fetuses
 Yale Students	 Females of childbearing potential	

NOTE: Is this research proposal designed to enroll children who are wards of the state as potential subjects? Yes No (If yes, see Instructions section VII #4 for further requirements)

Subjects must pass the following quiz (80% correct) in order to be eligible to consent for the study.

1. I will take study medication for 52 weeks/1 year in this study.	T_X_	F ____
2. This study aims to help me lose weight.	T_X_	F ____
3. I have to be in the study, even if I don't want to.	T ____	F_X_
4. I will have blood drawn in this study.	T_X_	F ____
5. I should report to the study doctor if I have any side effects	T_X_	F ____
6. I will be paid for study assessments.	T_X_	F ____
7. The study doctor and research team will know which medication I'm taking during the study.	T ____	F_X_
8. Please circle the names of the study medication that you may receive in this study.		

Haldol

Prolixin

Mellaril

Naltrexone

Paxil

Placebo

9. I can stop being in the study any time that I want.	T_X_	F ____
10. One of the possible side effects of the study medication is nausea.	T_X_	F ____
11. If I take the study medication while taking an opiate (see list on last page) I may experience withdrawal symptoms, such as nausea, vomiting, diarrhea, muscle aches, abdominal cramping, anxiety, and sweating.	T_X_	F ____

7. Inclusion/Exclusion Criteria: What are the criteria used to determine subject inclusion or exclusion?

Inclusion Criteria

- 1) Age 18 to 75
- 2) Meet DSM-IV criteria for schizophrenia, schizoaffective disorder, bipolar disorder, major depression, or another psychotic disorder based on SCID interview
- 3) Body Mass Index (BMI) of 28 and over

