Hypothesis Testing: The primary goal of this study is to compare the weight changes resulting from two different doses of naltrexone compared to placebo. The primary ITT analysis will employ a linear mixed effects model (LMM) to determine the effect of treatment status (between-subjects for: naltrexone 25/50mg vs. placebo) on the trajectory of weight change over time (within-subjects for: study time points). The interaction between treatment and time will be modeled and interpreted using graphical displays and post-hoc contrasts on least square means. The latter will include estimation of group contrasts at each time point and polynomial (linear, etc.) contrasts for time within each group. However, the primary contrasts will be each dose compared with control at 52 weeks. Because the outcome data are correlated (i.e., weight assessed from the same subject at different time points), weight over time will be modeled through the inclusion of random subject effects and/or structured variance-covariance matrices, with the best-fitting structure determined by Bayesian-Schwartz Information criteria (BIC). Supportive analyses will also include covariate adjustment for clinically significant variables (as determined from baseline evaluations and also other treatment variables, such as sessions attended). The above model will be fit using SAS PROC MIXED (Cary, NC), using restricted maximum likelihood (REML). The effect of treatment assignment on the secondary outcomes, such as BMI, waist circumference, serum lipid profile, fasting glucose, and glycosylated hemoglobin (HbA1c) will be evaluated using the linear mixed modeling approach described above. The proportion of subjects achieving 3, 4, or 5% weight loss will be compared between the treatment groups with the Fisher's Exact test. Type 1 error for secondary outcomes will be adjusted using the Bonferroni correction, basing the adjustment on the number of conceptually related statistical tests.

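### The primary week-52 contrast is not stated to be a difference in change from baseline; taken literally it compares raw weight, which is valid but less precise

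*Combined protocol and SAP*

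**What the plan says.** All of the relevant text is in Section V, item 12 (Statistical Considerations), except the randomisation factors.

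- **Wording that points to change.** The primary goal is to "compare the weight changes resulting from two different doses of naltrexone compared to placebo", and the model is to estimate the effect of treatment "on the trajectory of weight change over time".
- **Wording that points to weight as the response.** On the correlation structure, the plan says that "weight over time will be modeled through the inclusion of random subject effects and/or structured variance-covariance matrices". The fixed effects described are treatment, time and their interaction.
- **The contrast.** The interaction is to be interpreted with post-hoc contrasts on least-squares means. "The latter will include estimation of group contrasts at each time point". The plan then adds: "However, the primary contrasts will be each dose compared with control at 52 weeks". No quantity is named.
- **Baseline.** Baseline variables that show clinically relevant group differences are to be adjusted for in supportive analyses. The primary model does not say whether intake weight is a response row, a covariate, or subtracted.
- **Randomisation.** The Research Plan (Section V, item 3) says: "Separate randomization schedules will be applied based on gender, and antipsychotic agent". Neither factor appears in the primary model.

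**The concern.** Three analyses fit this text:

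(a) change from baseline as the response, with the arms compared at week 52;

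(b) weight as the response with week 0 included, and a week-52-minus-week-0 interaction contrast, which is also a difference in change;

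(c) weight as the response, with a simple difference in least-squares means at week 52.

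Readings (a) and (b) are sound. Reading (c) is the literal one: a group contrast at a time point, from a model of weight, without baseline adjustment. It compares the mean body weight of different people, so the spread in how heavy they were at entry stays in the standard error. This is the primary analysis, so the precision of the main result turns on a choice that the plan leaves open and that could be made after the data are seen.

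**Working it through.** The documents give a sample size but no planned effect, SD, power or dropout rate, so the plan has no figure of its own to reproduce. The check is how much less precise reading (c) is.

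**Inputs from the documents.** 200 subjects randomised 1:1:1, taken as 66 per arm; two-sided 5% (Section V, items 3, 5 and 12). The pilot reports baseline weight as uncorrelated with weight change (Section V, item 2).

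**Assumed inputs.** Baseline SD (SDb) 15-25 kg; one-year SD of change (SDc) 5-8 kg, with 10 kg as a wider case; no dropout.

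**Step 1: when is raw weight worse?** With equal variances at baseline and week 52 and correlation ρ, SD of change = SD of weight × √(2(1−ρ)). So SE(raw)/SE(change) = 1/√(2(1−ρ)).

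| ρ | 0.50 | 0.80 | 0.875 | 0.90 | 0.95 | 0.98 |
|---|---|---|---|---|---|---|
| ratio | 1.0 | 1.6 | 2.0 | 2.2 | 3.2 | 5.0 |

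The raw contrast is less precise whenever ρ exceeds 0.5.

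**Step 2: size under the assumed SDs.** With baseline uncorrelated with change, SD(raw at week 52) = √(SDb² + SDc²), SE = SD × √(2/66) = SD × 0.174, and the ratio is √(1 + (SDb/SDc)²).

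| SDb (kg) | SDc (kg) | SE raw (kg) | SE change (kg) | Ratio |
|---|---|---|---|---|
| 15 | 5 | 2.75 | 0.87 | 3.2 |
| 25 | 5 | 4.44 | 0.87 | 5.1 |
| 15 | 8 | 2.96 | 1.39 | 2.1 |
| 25 | 8 | 4.57 | 1.39 | 3.3 |
| 15 | 10 | 3.14 | 1.74 | 1.8 |
| 25 | 10 | 4.69 | 1.74 | 2.7 |

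Under the equal-variance form of step 1 the ratio is simply SD(weight)/SD(change): 15/8 = 1.9 to 25/5 = 5.0, and 15/10 = 1.5 to 25/10 = 2.5 for a change SD of 10 kg. The two forms together give roughly 2-5, and 1.5-2.7 in the wider case.

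**Step 3: do random subject effects rescue reading (c)?** No. With complete data and unconstrained arm-by-visit means, the variance of the contrast at week 52 is (2/n) × the total variance of weight at week 52. A random intercept labels part of that variance as between-person but does not take it out. A check on the planned visit schedule (200/3 per arm; random intercept and slope; 1 kg residual SD) gave:

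| SDb, SDc (kg) | SE raw (kg) | SE change (kg) | Ratio |
|---|---|---|---|
| 15, 7.5 | 2.89 | 1.30 | 2.2 |
| 20, 6 | 3.61 | 1.04 | 3.5 |
| 20, 7 | 3.66 | 1.21 | 3.0 |
| 25, 5 | 4.41 | 0.87 | 5.1 |

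The baseline-adjusted contrast had the same SE as the change contrast to two decimals.

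**Step 4: dropout.** If week 0 is a response row, subjects who leave early still inform the between-person part. With m of n subjects per arm remaining, the per-arm variances are SDb²/n + SDc²/m (raw) and SDc²/m (change), so the ratio is √(1 + (m/n)(SDb/SDc)²). With an assumed 40% lost straight after baseline, 15/8 falls from 2.1 to √(1 + 0.6 × 3.52) = 1.8, and 25/5 falls from 5.1 to √(1 + 0.6 × 25) = 4.0.

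**Step 5: illustration in power.** The pilot difference is 2.45 + 0.47 = 2.92 kg. With power = Φ(d/SE − 1.96) + Φ(−d/SE − 1.96), change SDs of 5-8 kg give 10-19% on raw weight and 55-92% on change. At 5.45 kg (4.98 + 0.47: the exploratory non-diabetic naltrexone mean, with the overall placebo gain assumed to apply), they give 22-51% and 97% or more. Both effects are 8-week pilot figures, not planning values for week 52.

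**The case against.** The strongest reply is that the plan already means change. Its stated goal and model target both say so. Hypothesis 1 is about reducing weight, the pilot is reported as kilograms lost or gained, and responders are defined by percentage weight loss. Modelling weight over time fits reading (b) as well as (c), and the treatment-by-time interaction is where differences in change sit. This stands as to intent. It does not settle the contrast, because the sentence that defines the primary comparison names no quantity and belongs to a family of group contrasts at single time points.

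Second, the factor of 2-5 cannot be derived from the documents. This stands. The only printed SDs of weight change are about 3 kg, from 8-week pilot subgroups. With 3.03 kg and an assumed raw SD of 15-25 kg the ratio would be 5.0-8.3, while a change SD of 10 kg brings it down to 1.5-2.7. Dropout also lowers it. The direction does not depend on these choices so long as the correlation exceeds 0.5, which is very plausible for adult weight over one year.

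Third, supportive covariate adjustment is planned. It is, but it does not change the primary result.

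A reader might go further and infer that no baseline weight will be available, because the Assessment Schedule row for weight does not name week 0. The documents do not support that: the Research Plan lists weight and height among the assessments that follow the intake sessions, and eligibility requires a BMI.

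**Conclusion.** The concern holds as a gap in the definition of the primary contrast. The plan does not say whether the week-52 comparison is of change or of weight, and it keeps baseline adjustment out of the primary model. Under the literal reading the standard error would be roughly 2-5 times larger, given an assumed baseline SD of 15-25 kg, an assumed change SD of 5-8 kg and no dropout. It would be about 1.5-2.7 times larger with a change SD of 10 kg, and somewhat less than these figures with dropout if week 0 is a response row.

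Two stronger conclusions are tempting and not supported. One is that the trial is set to run an inefficient analysis and is therefore underpowered: the stated goal makes that reading the less likely one, and no effect or SD is given from which power could be fixed. The other is that the result would be biased: under randomisation both scales estimate the same expected treatment difference, so the cost is precision and exposure to chance imbalance in baseline weight.

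It should still be fixed, because it concerns the primary analysis and a better-specified model costs almost nothing.

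**What to change.** Define the primary contrast as the week-52 difference, each dose versus placebo, in change in weight from baseline. Then name one way to fit it:

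- change as the response at post-baseline visits, with baseline weight and baseline-by-visit as covariates; or
- weight as the response with week 0 as a response row, and either a common baseline mean across arms or a difference-in-change contrast.

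Also include gender and the antipsychotic stratum, as used for randomisation, as fixed effects in the primary model. The gain is small, but it makes the analysis match the randomisation. Other covariate adjustment can stay supportive, as planned. The same statement of scale should carry over to BMI, waist circumference and the laboratory outcomes, which use the same modelling approach.

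The cost is one sentence on the scale, a few model terms and a few degrees of freedom. Every variable needed is already collected.

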Data will be electronically scanned into databases and will be double checked by hand. Hard copy documents will be examined to verify questionable observations. Missing data will be examined for each variable. Histograms, normal probability plots, and numerical summaries (skewness, kurtosis) will be used to examine distributional assumptions required for the mixed model analysis described below. Transformations such as the logarithm, square root, and reciprocal will be considered in the event the normality assumption is inadequate. Residual analysis will also be performed to evaluate distributional variance and linearity assumptions. Data analysis will be conducted in collaboration with [name], statistician in the department of Psychiatry and [name] faculty member of the Department of Biostatistics at Yale University School of Public Health. For all analyses, an alpha threshold of 5% (two-sided) will be used to test for statistical significance and will be performed using SAS v9.3 (SAS Institute, Cary, NC).

Analyses will be performed according to the intent-to-treat (ITT) principle where data from any randomized subjects will be analyzed. We will calculate descriptive statistics for participants at baseline, and compare naltrexone to placebo participants using analysis of variance (ANOVA) for normally distributed covariates and chi-square tests for categorical covariates. The impact of baseline variables that demonstrate clinically relevant group differences will be assessed in supportive analyses using covariate adjustment.

Approach to Missing Data: The primary analysis method will use a likelihood-based mixed model, which accommodates incomplete observations and operates under the assumption that the missing data is missing at random (MAR). Missing data patterns, time to withdrawal and reasons for dropout will be compared between the two naltrexone and placebo groups. T-tests, cross-tabulations, and logistic regression will be used to evaluate whether withdrawal is dependent on any observed variables. Finally, should missing data patterns and reasons for missing data suggest a bias or confounding, we will conduct sensitivity analyses using pattern mixture models to examine the influence that dropout bias (informative missingness) may have on treatment differences. Multiple imputation (MI) will also be used in the case of data not MAR. Sensitivity analyses will be performed secondarily among study completers.

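### Supportive treatment-effect models may adjust for sessions attended, a post-randomisation variable, so the adjusted estimate need not target the ITT effect

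*Combined protocol and SAP*

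**What the plan says.** All of the relevant analysis text is in Section V, item 12 (Statistical Considerations).

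- **Analysis principle:** "Analyses will be performed according to the intent-to-treat (ITT) principle where data from any randomized subjects will be analyzed".
- **Primary comparison:** the primary model is a linear mixed model of weight over time, and "the primary contrasts will be each dose compared with control at 52 weeks". It is not stated to include attendance.
- **Baseline paragraph:** "The impact of baseline variables that demonstrate clinically relevant group differences will be assessed in supportive analyses using covariate adjustment".
- **Hypothesis Testing paragraph:** "Supportive analyses will also include covariate adjustment for clinically significant variables", with those variables chosen "as determined from baseline evaluations and also other treatment variables, such as sessions attended".
- **Missing-data paragraph:** "Missing data patterns, time to withdrawal and reasons for dropout will be compared between the two naltrexone and placebo groups".

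The plan does not define sessions or list the other treatment variables. It does not say what quantity the attendance-adjusted model estimates, and it does not label that model exploratory. Two readings of sessions are possible. The Research Plan (Section V, item 3) has subjects seen weekly for four weeks, and "thereafter they will be seen on a bi-weekly (every other week) basis to be assessed (i.e. weight, side effect check, paper questionnaires") up to week 52. The same item names a SIMPLE intervention once, in its description of the BPRS, without a session schedule.

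**The concern.** Attendance builds up over the 52 weeks after assignment, so treatment can influence it. The Risks section (Section V, item 9) makes such a route plausible: it lists nausea (10%), headache (7%) and dizziness (4%) from an open-label naltrexone study. Attendance may also respond to how a subject's weight is going, and it overlaps with dropout, so adjusting for it partly conditions on follow-up.

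In any of these cases the treatment coefficient adjusted for attendance answers a different question from the ITT contrast. The model is called supportive, so a reader may take it as strengthening or weakening the primary result. If the estimate moves after adjustment, the model alone cannot show whether the covariate caused the movement. What is at stake is how one supportive estimate is interpreted.

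**Working it through.** The plan states no figure on this point, so there is none to reproduce.

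**Inputs from the documents:** 200 subjects allocated 1:1:1, so 200/3 ≈ 67 per arm; two-sided alpha of 5%; 4 weekly visits plus 48/2 = 24 fortnightly visits, so 28 visits. **Assumed inputs:** every attendance gap, correlation and dropout rate below. All shifts are in units of the within-arm SD of week-52 weight change.

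**1. When the estimate moves.** Let T be the arm, S attendance (within-arm SD 1) and U an unmeasured common cause, with S = g·T + r·U + error and Y = direct·T − b·S − c·U + error. The total effect is direct − b·g. Given T and S, the expected value of U is r(S − g·T). The coefficient of T adjusted for S is therefore

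total effect + g(b + c·r).

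The shift is zero if g = 0 (assignment does not affect attendance), and it can have either sign. With pre-randomisation covariates only, the shift is zero in expectation.

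**2. Single regression at week 52 (not the planned model).** Take b = 0, no true effect, and a common cause correlated r with both attendance and weight change. Attendance and weight change then correlate at r², and the shift is gap × r². Results from 40,000 simulated trials per setting:

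| r | Attendance gap (SD) | Gap × r² | Simulated shift | False positives |
|---|---|---|---|---|
| 0.3 | 0 | 0 | 0.000 | 5.0% |
| 0.3 | 0.2 | 0.018 | 0.018 | 5.1% |
| 0.3 | 0.5 | 0.045 | 0.044 | 5.7% |
| 0.5 | 0.2 | 0.050 | 0.050 | 5.9% |
| 0.5 | 0.3 | 0.075 | 0.075 | 7.2% |
| 0.5 | 0.5 | 0.125 | 0.125 | 11.1% |

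At r = 0.4 with a gap of 0.5 the shift is 0.5 × 0.16 = 0.080, and false positives are also about 7%.

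**3. Mixed model, 28 visits, complete data.** The range runs from (r, gap) = (0.3, 0.2) to (0.5, 0.5).

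- Attendance as a main effect, compound symmetry: 0.008 to 0.059.
- Attendance as a main effect, random slope: 0.001 to 0.004.
- Attendance-by-time term: 0.016 to 0.121.

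Hand check of the first line: the visit weeks sum to 706, so the mean visit is at 706/28 = 25.2 weeks, or 25.2/52 = 0.485 of the year. If the common cause acts on weight linearly over time, a constant attendance term picks up about that fraction of the week-52 shift. That gives 0.018 × 0.485 = 0.009 and 0.125 × 0.485 = 0.061, close to the simulated values.

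**4. Closest to the plan: mixed model with random slope, attendance counted from simulated dropout.** Dropout depends on observed weight change and on arm. Assumed retention is 63–66% against 44–47%, an attendance gap of 0.35 SD, with no true effect and 400 trials.

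- Main effect: shift 0.012 to 0.024.
- Attendance-by-time term: shift 0.044 to 0.086.
- False positives: 5.5–6.2% adjusted and 5.5–7.0% unadjusted. The simulation error is √(0.05 × 0.95/400) ≈ 1.1 percentage points, so these do not differ clearly.

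**5. Attendance only responds to weight change.** Here r is the direct correlation between attendance and weight change. The single regression removes a share r² of a true effect: 9, 16 and 25% at r = 0.3, 0.4 and 0.5. A true effect of 0.50 SD was estimated as 0.456, 0.419 and 0.376. In the dropout-based mixed model the share removed is 0.4–1.0% (main effect) or 1.2–5.0% (attendance by time).

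**The case against.** The strongest reply is that the model has little weight. The plan already ranks its analyses: a primary ITT model, primary contrasts at 52 weeks, then supportive analyses, and attendance appears only in the last. That stands, and it limits the point to interpretation.

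Three further replies also stand.

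- The inputs are assumed, and some are strong. The only dropout figure in the documents is the pilot's 1 of 24 subjects over 8 weeks, on placebo (Section V, item 2). That trial was short, but nothing documented supports a retention gap of about 19 points. The side-effect rates come from an open-label study in alcoholism without an arm comparison.
- A reader might infer that the two paragraphs on covariate adjustment contradict each other. They do not: the baseline paragraph never says that only baseline variables may be used, and the later paragraph adds to it.
- An attendance analysis can be a legitimate exposure question, so a ban is not needed.

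One part remains unanswered. The plan puts a post-randomisation covariate in the same supportive model class as baseline covariates, with an open-ended list and no separate estimand. The planned comparison of withdrawal between groups does not change what the adjusted coefficient estimates.

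**Conclusion.** The point holds as a free improvement. Followed as written, the plan can produce a supportive estimate that does not target the ITT effect, under either reading of sessions. This happens only if assignment affects attendance and attendance is related to weight. The documents do not show whether it would happen, in which direction, or how far.

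Under the assumed inputs, the model closest to the plan shifts by about 1 to 2% of an SD with no clear rise in false positives. Two stronger inferences are not supported.

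- A reader might take the shift of about 12% of an SD, or the 11% false-positive rate, as the expected harm. The false-positive figure comes from a single week-52 regression. The larger shifts come from that regression or from an attendance-by-time term. The plan states neither.
- A reader might infer that the trial's main result is compromised. The primary 52-week contrasts and the baseline-adjusted models do not use attendance, and no decision in the plan rests on the attendance-adjusted model.

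**What to change.** In the Hypothesis Testing paragraph of Section V, item 12, remove the clause that admits other treatment variables and sessions attended. Supportive treatment-effect models would then adjust for pre-randomisation variables only, in line with the baseline paragraph of the same item.

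If an attendance analysis is wanted, keep it as a separate analysis, define what counts as a session, and label it exploratory and not an estimate of the ITT effect. Report attendance by arm descriptively, beside the comparison of time to withdrawal and reasons for dropout that is already planned.

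The cost is one clause removed and one descriptive row added. No new data, subjects or visits are needed, and the primary analysis does not change.
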